7.0 Inclusion and Exclusion Criteria

7.1 Eligibility Criteria: Describe the criteria that define who will be included or excluded in the final study sample. If the study design includes multiple groups, be sure to list the criteria for each group.

Inclusion Criteria:

Participants 13.00-21.99 years old

Participants with a physician confirmed T1D diagnosis

T1D diagnosis was at least 6 months prior to study enrollment

Participants are on an intensive insulin regiment (either with an insulin pump or multiple daily injection)

Participants must be using a continuous glucose monitor (CGM)

Participants and parents/LARs of participants less than 18.00 speak/read English

Participants must have regular access to a smart device capable of Wi-Fi or data usage

Exclusion Criteria:

Participants with evidence of type 2 or monogenic diabetes.

Participants with a comorbid chronic condition (e.g., renal disease).

Participants with presence of severe psychiatric disorders.

Participants with a diagnosis of low vision (vision that cannot be corrected with contact lenses or eyeglasses).

Participants with limited mobility that would prevent participant from engaging in daily physical activity, self-assessed by participant.

7.2 Equitable Selection: Inclusion/exclusion criteria should be both fair and appropriate to the research question. If your study involves inclusion/exclusion criteria based on demographic characteristics such as sex, race/ethnicity, language, provide rationale for the criteria. For example, if excluding non-English speaking subjects, provide rationale for why it is not possible to include non-English speaking subjects.

This is a small test of change in preparation for future studies that will include non-English speaking populations.

targeted for enrollment into the study]: (Members of the following populations may not be included as subjects in the research unless selected here.)
☐ Children/Minors (under 7 years of age)
☐ Children/Minors (7-17 years of age)
☐ Neonates (infants less than 30 days old)
☐ Neonates of Uncertain Viability (infants less than 30 days old)
☐ Non-Viable Neonates (infants less than 30 days old)
☐ Wards of the State
☐ Fetuses

⊠Pregnant Women
☐ Adults with impaired decision-making capacity
☐ CM Employees
☐ CM Students/Residents/ Fellows
☐ Economically or Educationally Disadvantaged Persons
☐ Prisoners

This study will be inclusive of adolescents from 13.00 to 17.99 years of age, a vulnerable population. This inclusion is important to research because T1D affects this age group and more information about PA and management of T1D is needed. Many of the procedures required to collect data as explained in Section 5.0, Study Design, of this protocol are aspects of routine T1D care for youth and thus the risk for coercion/harm in participation is low. Informed assent of adolescents 13.00 to 17.99 will be obtained per CM policy and parental/LAR permission assent will be obtained for all participants in that age group as explained in Section 9.0, Screening and Recruitment Methods, in this protocol.

If an adolescent subject reaches the age of 18.00 during study participation, he or she will be asked to reconsent as an adult to further participation. If active participation is complete, consent will not be reobtained.

Pregnant women may participate as there is no risk beyond that of PA within healthy guidelines and will be set in collaboration with the participant.

8.0 Local Number of Subjects

8.1 Indicate the total number of subjects or charts to be enrolled locally as well as the accrual goal. If the study includes multiple groups or cohorts, be sure to describe the number of subjects required for each cohort. If one of the groups includes a chart review, each chart is considered a subject and needs to be reflected in the numbers below.

Target sample size is one group of 50 participants.

	Group 1	Group 2	Totals
Accrual Goal:	50	NA	
The number of evaluable subjects/charts you are targeting for the required			

andraint for the		
endpoint for the		
study.		
This number		
typically is based		
on statistical input		
such as a power		
analysis.		
_		
Anticipated	70	
Anticipated	/0	
Enrolled/Consented:		
This is the		
number reported		
at Continuing		
Review.		
Estimated number		
of subjects/charts		
that you anticipate		
you will need to		
enroll in order to		
meet your accrual		
goal above.		
This can generally		
be calculated as		
accrual goal +		
number of		
anticipated screen		
failures + number		
of potential		
withdrawals/drop		
outs.		
A (1.70	250	
Anticipated Pre-	250	
	250	
Screened (if applicable):	250	
Screened (if applicable): Estimated number	250	
Screened (if applicable): Estimated number of subjects/charts	250	
Screened (if applicable): Estimated number of subjects/charts you anticipate you	250	
Screened (if applicable): Estimated number of subjects/charts you anticipate you will screen prior to	250	
Screened (if applicable): Estimated number of subjects/charts you anticipate you will screen prior to	250	
Screened (if applicable): Estimated number of subjects/charts you anticipate you will screen prior to obtaining	250	
Screened (if applicable): Estimated number of subjects/charts you anticipate you will screen prior to obtaining permission/assent/	250	
Screened (if applicable): Estimated number of subjects/charts you anticipate you will screen prior to obtaining permission/assent/consent.	250	
Screened (if applicable): Estimated number of subjects/charts you anticipate you will screen prior to obtaining permission/assent/consent. For example, if	250	
Screened (if applicable): Estimated number of subjects/charts you anticipate you will screen prior to obtaining permission/assent/consent. For example, if your study	250	
Screened (if applicable): Estimated number of subjects/charts you anticipate you will screen prior to obtaining permission/assent/consent. For example, if your study includes a review	250	
Screened (if applicable): Estimated number of subjects/charts you anticipate you will screen prior to obtaining permission/assent/consent. For example, if your study includes a review of medical records	250	
Screened (if applicable): Estimated number of subjects/charts you anticipate you will screen prior to obtaining permission/assent/consent. For example, if your study includes a review of medical records to identify	250	
Screened (if applicable): Estimated number of subjects/charts you anticipate you will screen prior to obtaining permission/assent/consent. For example, if your study includes a review of medical records to identify	250	
Screened (if applicable): Estimated number of subjects/charts you anticipate you will screen prior to obtaining permission/assent/consent. For example, if your study includes a review of medical records to identify potential	250	
Screened (if applicable): Estimated number of subjects/charts you anticipate you will screen prior to obtaining permission/assent/consent. For example, if your study includes a review of medical records to identify potential participants prior	250	
Screened (if applicable): Estimated number of subjects/charts you anticipate you will screen prior to obtaining permission/assent/consent. For example, if your study includes a review of medical records to identify potential participants prior to obtaining	250	
Screened (if applicable): Estimated number of subjects/charts you anticipate you will screen prior to obtaining permission/assent/ consent. For example, if your study includes a review of medical records to identify potential participants prior to obtaining permission/assent/	250	
Estimated number of subjects/charts you anticipate you will screen prior to obtaining permission/assent/ consent. For example, if your study includes a review of medical records to identify potential participants prior to obtaining permission/assent/ consent, this	250	
Estimated number of subjects/charts you anticipate you will screen prior to obtaining permission/assent/ consent. For example, if your study includes a review of medical records to identify potential participants prior to obtaining permission/assent/ consent, this number would be	250	
Estimated number of subjects/charts you anticipate you will screen prior to obtaining permission/assent/consent. For example, if your study includes a review of medical records to identify potential participants prior to obtaining permission/assent/consent, this number would be the estimated	250	
Screened (if applicable): Estimated number of subjects/charts you anticipate you will screen prior to obtaining permission/assent/consent. For example, if your study includes a review of medical records to identify potential participants prior to obtaining permission/assent/consent, this number would be	250	
Estimated number of subjects/charts you anticipate you will screen prior to obtaining permission/assent/ consent. For example, if your study includes a review of medical records to identify potential participants prior to obtaining permission/assent/ consent, this number would be the estimated number of records	250	
Estimated number of subjects/charts you anticipate you will screen prior to obtaining permission/assent/ consent. For example, if your study includes a review of medical records to identify potential participants prior to obtaining permission/assent/ consent, this number would be the estimated number of records you anticipate you	250	
Estimated number of subjects/charts you anticipate you will screen prior to obtaining permission/assent/ consent. For example, if your study includes a review of medical records to identify potential participants prior to obtaining permission/assent/ consent, this number would be the estimated number of records you anticipate you will need to review	250	
Estimated number of subjects/charts you anticipate you will screen prior to obtaining permission/assent/ consent. For example, if your study includes a review of medical records to identify potential participants prior to obtaining permission/assent/ consent, this number would be the estimated number of records you anticipate you	250	

9.0 Screening and Recruitment Methods

9.1 Screening and Identification of Potential Subjects:

How will subjects be identified? (Check all that apply) □ Chart reviews ☐ After obtaining permission/assent/consent ☑ Prior to obtaining permission/assent/consent (Pre-Screening) *NOTE: If pre-screening, you must address Partial Waiver of HIPAA Authorization below in the "HIPAA & Confidentiality" section. ☑ Through Cerner or other CM sources (e.g. databases, billing records, pathology reports, admission logs, etc.) May involve access of records by individuals not involved in the patient's care. ☑ List of candidates provided through the Data Report Request Form By their treating physician who will then provide the study team's contact information to the potential subject/family By their treating physician who will obtain patient/family permission to share contact information with the study team ⊠ Self-refer in response to IRB approved advertisements or websites ☐ Subjects will roll-over from another research study: Study # ⊠ Registry of individuals interested in research opportunities ☐ Past subject list \square Other:

9.2 Recruitment of Potential Subjects:

In clinic, telephone, partial waiver of HIPAA authorization for pre-screening/recruitment only.

Study staff will pre-screen potentially eligible youth and YAs to see if they meet enrollment criteria. Study staff may contact families who appear to meet criteria by reaching out via phone or CM approved conferencing platform and approaching families during a standard of care visit to receive information about this study. If no one answers the phone, only up to 3 voicemails will be left per potential participant and will be tracked on the Pre-screening Log. Recruitment may also involve a report generated by IT that will involve a review of the electronic medical record (EMR) system to generate a list of potentially eligible families. Potential participants may also learn of the study through the intake form, Find A Study page, or the study flyer. The flyer can be posted on the Diabetes Clinic intake form that families complete before appointments or in

clinic spaces. The flyer and Study Information Sheet can be posted on the hospital's Find a Study page.

Study staff will provide youth and their parent/LAR and YA participants information about the study and answer any questions they may have in order to help them determine if they would like to participate as explained in Section 5.0, Study Design. Participants and parents/LARs of youth will have ample time to bring forward any questions or concerns during the period between recruitment contact and the e-consent process. Participants and parents/LARs will be presented with all study information during the e-consent process. At that time informed parental/LAR permission and/or participant assent/consent will be obtained. Study staff will take care to answer all questions and place no pressure on any potential participant or their parent/LAR to enroll.

To minimize risk, we will inform all participants, and parents/LARs of adolescent participants, that they do not have to participate and that a decision not to participate will not affect their care at CM. We will inform all participants and parents/LARs of adolescent participants of the risk of breach of confidentiality as well as these steps we will follow to reduce the risk of a breach of confidentiality and to protect their privacy (e.g., limiting access to data, de-identifying data, securing data in a secure CM network drive). We will inform participants that they can refuse to answer any question during the study. Similarly, we will inform participants that they can refuse to participate in any component of the study protocol and withdraw from the study at any time without penalty or loss of benefits.

We request a HIPAA waiver for the purpose of generating pre-screening lists of qualified candidates for research recruitment as described above. Study staff will record information collected for the purposes of recruitment in the pre-screening log (e.g., eligibility met, contact information, clinic visits where study staff may approach families). Study staff will store personal health information (PHI) on non-participants until completion of enrollment. Study staff will do this to reduce the likelihood of re-approaching families or YAs who have already declined participation in the study. Upon the completion of enrollment, the study team may request a de-identified, aggregate report containing demographic information on individuals who declined enrollment. Study staff may use this information to compare recruited individuals to non-recruited individuals in dissemination work products (e.g., manuscripts, presentations) so that we can report any biases in sampling the eligible populations. Additionally, PHI such as name, age, etc. will be kept on the enrollment log until study completion at which time, that information will be destroyed.

10.0 Procedures

10.1 Provide a description of research procedures of all research procedures being performed and when they are performed, including procedures being performed to monitor subjects for safety or minimize risks.

We will recruit eligible pediatric patients from the Pediatric Diabetes Clinic at Children's Mercy-Kansas City (CM) as explained in Section 9.0, Screening and Recruitment Methods of this protocol. We will use a tablet and/or computer and REDCap to collect family survey data, collect information from participant's Electronic Health Record (EHR) upon agreement to participate, and instruct participants in how to wear the actigraph and the actiwatch and track, and share data with the research team as explained in Section 5.0, Study Design of this protocol. Contact with participants via phone/email is explained in detail as well in Section 5.0. This study involves no more than minimal risk and procedures to minimize any potential risk to participants is also explained in Sections 5.0, 9.0 under subheading 9.2, and 15.0 of this protocol.

Visit 1:

Informed permission/assent/consent (PAC) from adult participant or child and parent/LAR will be obtained prior to study procedures being performed. All required elements of PAC will be documented in REDCap as this study will not be in the medical record per CM policy.

The study team will conduct a medical chart review to collect demographic information including date of birth, age, gender, height, weight, race, ethnicity, medical history, date of T1D diagnosis, treatment regimen, T1D-related hospitalizations, number of contacts and visits with clinic staff.

HbA1c is a proxy measure of glycemic control over the past 12 weeks. HbA1c will be collected from medical record via POC measures collected during routine diabetes clinic visits.

Glucometer, CGM, and/or pump uploads from SOC visits may be included to assess frequency of blood glucose checks or insulin delivery as a proxy measure of self-management adherence. We may also calculate mean daily blood glucose, percent high BG, percent low BG, and percent in range for glucose levels²¹, and insulin BOLUS scores²² from participants' device uploads.

Baseline Surveys will be sent to participants via REDCap after informed e-consent PAC is completed. This will include Demographics, Treatment Self-Regulation Questionnaire (Exercise), Treatment Self-Regulation Questionnaire (Diet), Perceived competence for Exercise Questionnaire, Social Support for Exercise Questionnaire, (Family), Social Support for Exercise (Friends), Physical Activity Self-Efficacy Questionnaire, and Physical Activity Attitudes Questionnaire, Power of Food Scale, and Pediatric Quality of Life (PedsQL) Parent Report.

We will collect an objective measure of participants' MVPA based on wrist-worn actigraphs and wrist-worn actiwatches. Youth and YAs with T1D who consent to participate will receive a GT3X actigraph and instructions how to share the data from their GT3X actigraph with the study team. Participants will also receive an actiwatch (Garmin Vivosmart 4 or higher as an additional measure of MVPA. We will use age-appropriate guidelines to identify and calculate daily minutes of MVPA.

We will ask participants to complete a PA calendar in order to track their scheduled PA. This activity calendar will be completed in REDCap. Participants will also answer an open-ended question "What would you like to set your initial baseline PA goal as in minutes?" to help to anchor PA goals for the NUDGE intervention.

Participants may complete questionnaires outlined in section 11.0 electronically with the survey links sent via email or text using Twilio. We will set up the distribution of the EMA REDcap Surveys to be completed 4 times per day with family and/or participants for seven days for the initial 7-day assessment with the actigraph and actiwatch. The EMA Survey includes Negative Affect Scale for Children Questionnaire, Latent Mood Questionnaire, Environment Questionnaire, and a sleep diary. The actigraph and actiwatches will be shipped within 10 days to participants with instructions on how to use both as well as how to return the devices at the end of seven days.

Visit 2:

Set up distribution of the EMA REDcap Surveys with family and/or participant 4 times per day for seven days. The actigraphs and actiwatches will be shipped within 10 days to participants with instructions on how to use the devices as well as how to return the devices at the end of seven days.

Visit 3:

Set up distribution of the EMA REDcap Surveys with family and/or participant 4 times per day for seven days. The actigraphs and actiwatches will be shipped within 10 days to participants with instructions on how to use the devices as well as how to return the devices at the end of seven days.

The REDcap Treatment Satisfaction Survey will be distributed to participants which includes the Client Satisfaction Questionnaire and the Exit Interview and Acceptability Questionnaire.

Returning Study Devices. We will use one of two procedures to facilitate the return of any study-specific devices. First, we will send participants/families a prepaid box in which to return all study-related devices to the research team. Second, if necessary, we may make arrangements to pick up devices during a routine T1D clinic visit.

Feasibility Assessment. We will evaluate feasibility based on: the percentage of time participants wore the actigraphs during the study period, the percentage of daily PA surveys adolescents completed, and the percentage of complete interactions with the NUDGE intervention.

Initial Efficacy Assessment. Refer to Section 4.0, Study Endpoints

11.0 Surveys and Psychometric Testing:

This study will include questionnaires to assess participants' motivation for beginning/continuing PA, belief in competency/efficacy in regard to PA, social support for engaging in PA, personal attitudes toward PA, satisfaction with the intervention and participation in the study, and what participants did or did not enjoy about this study/intervention. Additionally, participants will be asked about their environment, emotional status, and changes in well-being due to intervention engagement. EMA REDcap Survey includes questions from two validated measures: The Positive and Negative Affect Scale for Children²³ and the Latent Mood Questionnaire²⁴. The other measures included in the Baseline survey have also been previously validated: Treatment and Self-Regulation Questionnaire²⁵, Physical Activity Attitudes Questionnaire²⁶, Perceived Competence for Exercise²⁷, Social Support for Exercise²⁸, the Physical Activity Self-Efficacy Questionnaire²⁹, Power of Food Scale³⁰, and Pediatric Quality of Life (PedsQL) Parent Report³¹.

Included in Baseline Survey:

Demographic Survey

Treatment Self-Regulation Questionnaires (Exercise & Diet). The treatment self-regulation questionnaires assess motivation for eating a healthy diet and engaging in healthy physical activity. This measure has 15-items that assess autonomous and controlled motivation for engaging in the behavior on a 7-point Likert scale (1= Not at all true, 7= Very true)²⁵.

Perceived competence for Exercise. The Perceived Competence for Exercise questionnaire is a 4-item scale that assesses an individual's perception of their own ability to exercise on a regular basis on a 7-point Likert scale (1= Not at all true, 7= Very true)²⁷.

Social Support for Exercise (Family). The social support for exercise questionnaire assesses to what degree family members provided support for the adolescent to be physically active. The measure is comprised of 13-items pertaining to support from friends and 13- items pertaining to support from family. Each item is scored on a 5-point scale (1= None, 5= Very often)²⁸.

Social Support for Exercise (Friends). The social support for exercise questionnaire assesses to what degree friends provided support for the adolescent to be physically active. The measure is comprised of 13-items pertaining to support from friends and 13-items pertaining to support from family. Each item is scored on a 5-point scale (1= None,

 $5 = \text{Very often})^{28}$.

Physical Activity Self-Efficacy Questionnaire. The physical activity self-efficacy questionnaire is an 8-item instrument used to determine the participant's perception of their own ability to be physically active. Each item is scored on a 5-point scale (1 =Disagree a lot, 5 =Agree a lot)²⁹.

Physical Activity Attitudes Questionnaire. The Physical Activity Attitudes Questionnaire is a 17-item measure used to assess adolescent's outcome expectancies for physical activity. The instrument has a positive (e.g., being active would give me more energy) and negative (being active would make me tired) outcomes scale. Each item is scored on a 5-point scale (1= Disagree a lot, 5= Agree a lot)²⁶.

Power of Food Scale. The Power of Food Scale focuses on the psychological appetite for food and the enjoyment of food. It has been confirmed as a useful measure of patient's appetite for food and related issues³⁰. The version used is a 30 measure scale, 15 focusing on general attitudes, and 15 focusing on attitudes toward food the day of the survey.

Pediatric Quality of Life (PedsQL) Parent Report. The PedsQL is a 23 item measure validated for 2-18 Y.O.s, focused on health-related quality of life measures. It is applicable to both populations with and without chronic diseases, and utilizes both self-reported information or parent proxy information³¹.

EMA REDcap Survey:

Positive and Negative Affect Scale for Children. The Positive and Negative Affect Scale for Children is a short form (10-items) of the well-validated Positive and Negative Affect Scale that has been adapted and validated for use in children and adolescents. Each item is scored on a 5-point scale (1= Not at all, 5= Extremely)²³.

Latent Mood Questionnaire. To assess a variety of mood states the current study makes use of the three highest loading items for six of the subscales from the Profile of Mood States scale. The constructs represented in the current project are: Anger-hostility, Depression-dejection, Fatigue-inertia, Tension-anxiety, Vigor-activity, and Friendliness. Each item is scored on a 5-point scale (1= Not at all, 5= Extremely)²⁴.

Environment Questions. To obtain information regarding the location of participants when beginning each EMA survey, five questions will be asked pertaining to location, vegetation, traffic, safety, and the weather.

Sleep Diary. To obtain basic questions about the sleep pattern of the previous night and day (length of sleep, any naps, nap lengths), and see if sleep was disturbed due to T1D management.

Treatment Satisfaction Survey:

Client Satisfaction Questionnaire (CSQ-8). The Client Satisfaction Questionnaire is an 8-item measure of client satisfaction with services they receive³².

Exit Interview and Acceptability Questionnaire. This measure assesses the participants experience of being in the study.

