4.2 Describe the primary and secondary safety endpoints. **NA**

5.0 Study Design

5.1 Study Design: *Describe and explain the study design.*

We propose to pilot NUDGE in youth with T1D and look at treatment effects after at least 3 months. We anticipate the entire pilot study will last 12 months.

5.2 Schema: a schema is a representation of your study design in the form of an outline or a model. Including a schema is not a requirement but can be valuable tool in the presentation of your study to the IRB. Consider adding a diagram that provides a quick "snapshot" of the study.

Study Visit Procedures

5.3 *Table of Events*

	Consent	Visit 1 (Day	Day 25	Visit 2 (Day	Day 85	Visit 3 (Day	Daily	PRN (SOC)
	(Day -10 to	1 to 7)		30 to 37)		90 to 97)		
	-5)							
I/E Criteria	X							
E-Consent PAC	Х							
Baseline Survey	Χ							

Medical Chart	Χ							
Review for								
demographics								
Medical Records	Χ							X
– HbA1c								
Medical Records	Χ						X	
device uploads								
PA Calendar	Χ							
PA Goal Set	Χ						X	
Actiwatch	Χ		Х		X			
Shipment								
Actigraph	Χ		X		X			
Shipment								
Participant		X		X		X		
wears Aciwatch								
Participant		Х		Х		Х		
wears Actigraph								
Participant to co		Х		X		Х		
mplete								
EMA REDcap Sur								
vey (7 days,								
4x/day)								
Treatment						X		
Satisfaction								
Survey and Post								
Survey								

All questionnaires are outlined in Section 11.0.

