24.0 Withdrawal of Subjects

24.1 *Describe the anticipated circumstances, under which subjects will be withdrawn from the research without their consent.*

The only foreseeable circumstances of withdrawal from the research without their consent would be subjects not meeting eligibility criteria.

24.2 *Describe any procedures for orderly termination.*

See Section 23.0, Provisions to Protect the Privacy Interests of Subjects, of this protocol for additional information and below in Section 24.3.

24.3 Describe procedures that will be followed when subjects withdraw from the research, including data retention plans or partial withdrawal from procedures with continued data collection.

Participants may withdraw from the study at any time, and this will not affect their medical care. Study staff will not collect any study-related data on participants after their withdrawal from the study. Data collected up to withdrawal will be included in the analyses, with the exception of those who are withdrawn from the study for not meeting eligibility criteria.

Also see Section 23.0, Provisions to Protect the Privacy Interests of Subjects, of this protocol.

DATA MANAGEMENT

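### Satisfaction and exit questionnaires are scheduled only at Visit 3, so participants who formally withdraw before then give no acceptability data and no reason for leaving

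*Combined protocol and SAP*

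**What the plan says.** The only satisfaction and acceptability instruments are the CSQ-8 and the Exit Interview and Acceptability Questionnaire. Together they form the Treatment Satisfaction Survey (Section 11.0). Section 10.1 mentions that survey under Visit 3 only: "The REDcap Treatment Satisfaction Survey will be distributed to participants which includes the Client Satisfaction Questionnaire and the Exit Interview and Acceptability Questionnaire". In the Table of Events (Section 5.3) its row has a single mark, at Visit 3 (Day 90 to 97).

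Section 11.0 says the study's questionnaires cover, among other things, "satisfaction with the intervention and participation in the study, and what participants did or did not enjoy about this study/intervention". It describes the exit questionnaire in one line: "This measure assesses the participants experience of being in the study".

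On withdrawal, Section 24.3 states: "Study staff will not collect any study-related data on participants after their withdrawal from the study". It also states: "Data collected up to withdrawal will be included in the analyses", with an exception for people withdrawn as ineligible. Section 24.2, on orderly termination, only cross-refers: "See Section 23.0, Provisions to Protect the Privacy Interests of Subjects, of this protocol for additional information and below in Section 24.3".

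**The concern.** An exit instrument that is given only at the last scheduled visit does not reach anyone who withdraws before that visit. Keeping the data collected up to withdrawal does not help, because neither the baseline survey nor the EMA survey contains a satisfaction or acceptability item. The gap cannot be repaired at analysis.

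This matters because Section 27.1 presents the study as a pilot for a larger one, and Section 3.1 justifies the mHealth approach partly by its expected acceptability to adolescents and young adults. The burden is considerable: two wrist devices in each of three wear weeks, EMA surveys four times a day in those weeks (4 × 7 × 3 = 84 prompts), and daily texts for up to four and a half months. The larger study needs to know whether that burden drives people out. Bot logs and wear time can show that a participant stopped, but not why.

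**Working it through.** **Document check.** For a participant who formally withdraws before Day 90:

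1. Baseline survey (Sections 10.1 and 11.0): demographics, motivation, competence, social support, self-efficacy, attitudes, Power of Food and PedsQL. No satisfaction item.
2. EMA surveys: affect, mood, environment and sleep. No satisfaction item.
3. Treatment Satisfaction Survey: not yet due.
4. At withdrawal: Sections 24.2 and 24.3 plan no form and no recorded reason.
5. After withdrawal: Section 24.3 stops collection.

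Such a participant contributes nothing on acceptability. Someone who leaves after Visit 3 but before four and a half months could already have answered.

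**How many people.** The plan states no withdrawal rate and no acceptability figure, so there is nothing to reproduce. Section 8.1 gives 70 consented and 50 evaluable:

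- 70 − 50 = 20, and 20/70 = 28.6%.

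The template text in Section 8.1 counts screen failures and dropouts together in that allowance. Hence 20 is an upper bound on planned withdrawals, not an estimate.

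**What the missing answers could do.** The following are assumptions: a satisfied/not-satisfied classification (the plan gives no CSQ-8 cut-off), 70 participants who have all been exposed to NUDGE, L leavers before Visit 3, and all 70 − L others responding, of whom s are satisfied. With the leavers' views unknown, the proportion among all 70 lies between s/70 (no leaver satisfied) and (s + L)/70 (every leaver satisfied).

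| Leavers L | Satisfied among responders | Lower bound | Upper bound |
|---|---|---|---|
| 20 | 45/50 = 90% | 45/70 = 64% | 65/70 = 93% |
| 10 | 54/60 = 90% | 54/70 = 77% | 64/70 = 91% |
| 5 | 58/65 = 89% | 58/70 = 83% | 63/70 = 90% |
| 20 | 40/50 = 80% | 40/70 = 57% | 60/70 = 86% |

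When reported satisfaction is high, most of the room for error lies below it. With 20 leavers and 90% reported, the figure for all 70 could be up to 25.7 points lower (90.0 − 64.3) but only 2.9 points higher (92.9 − 90.0). With 5 leavers the margins are 6.4 and 0.8 points.

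**The case against.** The strongest reply is that no stated conclusion rests on this survey. Hypothesis 1 judges feasibility by the share of daily texts exchanged. The other feasibility measures are actigraph wear and completion of the daily PA surveys or schedules, and efficacy rests on MVPA, sedentary time and HbA1c. Section 27.1 does not mention satisfaction. All of this stands: the gap limits descriptive information for the next study and changes no primary result.

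Four stronger readings are tempting, and the documents do not support them.

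- *Everyone who disengages is missed.* Section 9.2 lets participants refuse any component without leaving the study. Someone who stops texting or wearing the devices but does not withdraw is still due the Visit 3 survey. The gap concerns formal withdrawal before that visit.
- *Section 24.3 forbids asking leavers.* It bars collection after withdrawal, not a question put when the request is made. The fault is that nothing plans the question.
- *Reported satisfaction is biased upward.* That is plausible, since dislike of the burden is a natural reason to leave. But the documents give no withdrawal reasons or rates, and the bounds above allow a small error in the other direction.
- *The plan expects 29% to drop out.* That share includes screen failures, who have no experience of NUDGE to rate.

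It is also fair to say that a voluntary exit form will have its own non-responders, and that a CSQ-8 completed after a few days of exposure is not comparable with one completed at Day 90. Both points shape the remedy but do not remove the need for it.

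**Conclusion.** The point holds within a limited scope. As written, acceptability data will come only from participants still enrolled at Visit 3, and no reason for earlier withdrawal will be recorded. The satisfaction results are likely, but not certain, to be favourable compared with the view of all enrolled.

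The size depends on an unstated number of early withdrawals: the possible distortion is substantial near the upper bound of 20 and small at 5. The percentages are bounds under assumed response figures, not predictions. The point is worth acting on because the remedy is cheap and the information cannot be recovered later.

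**What to change.** In Section 24.3 and the Table of Events, add wording such as: *At a request to withdraw before Visit 3, the participant is offered, as a voluntary last study contact before withdrawal takes effect, the Treatment Satisfaction Survey with its existing payment and one question on the reason for withdrawal.* Put matching wording in the information letter. Do not trigger the survey when someone merely stops using NUDGE, because that person still receives it at Visit 3.

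In Section 27.1, state that satisfaction will be reported separately for Visit 3 responders and early withdrawals, without pooling, and that each group's number answering will be shown against the number enrolled.

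Cost: a small amendment, since Section 21.1 requires IRB review of protocol changes and patient-facing material, and a REDCap trigger for a survey that already exists. Payment is up to $50 per early leaver, already a line within the $648 maximum in Section 18.1, so at most 20 × $50 = $1,000. Response among leavers will be incomplete. No sample-size figure changes.
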